## LIST OF ABBREVIATIONS

ACP- Amplatzer cardiac plug

AF- atrial fibrillation

ASA- aspirin

CTA- CT angiography

DAPT- dual anti platelet therapy

DAT- device associated thrombus

DEA- **Dabigatran Etexilate followed by Aspirin**

DOAC- direct oral anticoagulant

DRT- device related thrombus

ICE- intra-cardiac echocardiography

LAA- left atrial appendage

LAAC- left atrial appendage closure

OAC- oral anticoagulation

TEE- trans-esophageal echocardiography

WAS- Watchman access sheath

## **1. Background and Study Rationale:**

Two years after FDA approval of the first left atrial appendage (LAA) closure device for the prevention of embolic stroke in patients with non-valvular atrial fibrillation, over 13,000 Watchman (Boston Scientific, Inc., Natick, MA) devices have been successfully implanted in the US. Post-approval prospective registry data in 3,822 consecutive cases demonstrated implantation was successful in 3,653 (95.6%), with a median procedure time of 50 min with the majority of operators new to the procedure (71%). Complications included 39 pericardial tamponades (1.02%), 3 procedure-related strokes (0.078%); 9 device embolizations (0.24%), and 3 procedure-related deaths (0.078%) [1]. The early phase PROTECT-AF complications topped 10%, but clearly as expertise in trans-septal access, and improvements in the delivery system and technique have evolved, total complications post implant have dropped to <3% in the EWOLUTION registry [2].

With proper patient selection, routine use of ultrasound to guide venous access, and a continued trend to implant without bridging anti-coagulation, expert centers may be able to reduce total acute complications below 1%. As a stroke prevention strategy, this could position LAA closure as a cost-effective consideration, potentially as first line therapy for many patients. Several landmark clinical trials are ongoing in the LAA occlusion space and will provide prospective randomized trial data on over 5000 patients closed with a variety of methods. The Amulet (Abbott Medical, Inc.) versus Watchman IDE clinical trial (clinical trials.gov # NCT02879448) has rapidly enrolled since opening in 2017 with a target enrollment of 1400 subjects and 300 roll-in cases. Subjects eligible for a Watchman LAA closure device are randomized 1:1 to Amulet or Watchman and followed for a minimum of 18 months for the endpoint of stroke or systemic embolism. Additionally, the surgical LAAOS-III trial is studying over 4000 patients undergoing open heart surgery with a history of AF, and randomized 1:1 to LAA excision, or no intervention on the LAA.

Anti-coagulation regimen and anti-platelet therapy post Watchman implant in the Amulet IDE is according to the FDA labeling for Watchman subjects, with a more variable strategy in the Amulet arm, including even DAPT alone (ASA 81mg plus Plavix 75mg minimum of 6 months, followed by ASA 81mg alone). Traditional or standard of care anticoagulation management following Watchman LAA closure device implantation includes oral dose adjusted warfarin INR 2-3 for 45 days after implant (unclear if this requires initiation of warfarin pre-procedure in patients who were intolerant to OAC). In addition, ASA 81mg is to be taken to 45 days when a follow up TEE is performed to assess leaks, device position or thrombus formation. Typically (in PROTECT and PREVAIL over 92% of subjects stopped OAC at 45 days), the FDA labeling is to initiate ASA 325mg daily with clopidogrel 75mg daily for up to 180 days post implant, then indefinite ASA 325mg daily is recommended.

Referrals for LAA closure for anti-coagulation failure (formation of thrombus in the LAA despite medical therapy, or recurrent embolic events or stroke while on OAC) are not

clearly outlined in any LAA closure clinical trial inclusion criteria. In our experience, these may actually be the patients who stand to benefit the most from removing or occluding the LAA. Two separate studies have shown over a 93% LAA closure efficacy rate, including a 2017 LAA closure study with long term CTA assessment on Atriclip (Atricure Inc., West Chester OH, USA) placed by thoracoscopic approach [4,5]. Prior formal studies of surgical methods have reached 60-70% closure rates at best, and incomplete surgical closure is associated with a higher rate of stroke [6]. Management immediately following LAA closure by an epicardial approach with Atriclip or surgical closure does not appear to require systemic anti-coagulation, though no prospective randomized data exists to support this claim.

Several retrospective studies were published in 2017 supporting the use of NOAC (novel oral anti-coagulant) or DOAC (direct oral anti-coagulant) for anti-coagulation post LAA device implant to reduce DAT. EWOLUTION reported a 1 year device associated thrombus rate of 3.7% with Watchman, independent of the post implant regimen, in which 73% of anti-coagulation 'contra-indicated' subjects were on anti-platelet regimens alone [2]. A separate study showed a 3.2% DAT rate with the Amplatzer Cardiac Plug (previous generation of the Amulet device under IDE trial in the US) [7]. While certainly not what the implanting physician hopes to see at the 45 days or 1 year follow up TEE, whether a DAT leads to clinical ischemic strokes as a whole has been difficult to determine. Standard practice has been to initiate short-term oral anti-coagulation and repeat the TEE in 6 weeks to ensure resolution, of a DAT, then return to anti-platelet therapy alone.

The process of complete endothelialization of a Watchman LAA closure device is poorly understood. Animal models suggest complete endothelialization may be complete within 6 weeks. Human autopsy examples show variable endothelialization at up to 9 months. A study in 2017 using CT angiography demonstrated contrast flow across 66% of LAA devices at 6 weeks, questioning if TEE at 6 weeks is really a suitable metric for 'closure' [8]. Likely this represents a slow leak through the fabric cap and not around the device, if the TEE shows no Doppler flow. We have seen several cases where follow up TEE missed a leak and an obvious gap with contrast filling a trabeculated LAA lobe was seen with CTA. Anti-coagulation was discontinued, but long-term studies are needed to evaluate the impact of this finding.

Event rates for bleeding after Watchman versus warfarin show superiority after 6 months when clopidogrel is discontinued. This is where the net clinical benefit of LAAC is seen, leading to improved long term outcomes and ultimately the rationale for FDA approval of the Watchman device. The role of dual anti-platelet therapy, or the use of 325mg ASA versus 81 mg ASA long term is not supported by any specific literature, and was carried over from previous trials with use of coronary stents, and PFO and ASD occluder devices. Once the LAA device has complete occlusion with no flow into the LAA and surface endothelialization, it is plausible that ASA 81mg is a sufficient recommendation long term. This has recently been established in European AF guidelines on LAA closure for patients contra-indicated to OAC, supporting single or dual anti-platelet therapy after implant.

However, this potentially sets up an increased risk of device associated thrombus (DAT). If an alternative post procedure regimen using 90 days of dabigatran plus 81mg ASA alone is employed, eliminating the use of clopidogrel, we may reduce both major bleeding events, and reduce device associated thrombus rates at 1 year follow up. It would not be expected to impact ischemic stroke rate, but this could be implied if fewer DAT are observed.

In conclusion, LAA closure is becoming a reasonable strategy for patients at high risk for stroke (CHADS 2 Vasc score 3-9) and high risk for bleeding on long term OAC (HAS BLED score 2-6). The FDA labeled strategy for medical management after Watchman implant is loosely supported scientifically, and still exposes patients to increased bleed risk up to 6 months after implant due to the use of DAPT. A shorter and simplified use of dabigatran BID for 90 days post LAAC with ASA 81mg, followed by ASA 81mg daily long term may reduce bleeding events, and have a beneficial impact on lowering the rate of DAT. Praxbind is a specific monoclonal anti-body available for dabigatran reversal. All study centers will have Praxbind available for use in the event of a major bleed, (i.e., subdural or intracranial bleed, or major bleed requiring transfusion), or in case of unexpected or emergent surgery.

## **2. Study design:**

Single arm, prospective unblinded study on post Watchman LAA closure device implant anti-coagulation management at a primary center (Vanderbilt Medical Center) and up to 5 additional high volume LAA implant centers. This trial will be designed to evaluate the use of dabigatran for 90 days post implantation of an LAA closure device (Watchman LAA Closure Device, Boston Scientific Inc.). The drug will be initiated on the morning following device implantation, taken BID per package insert dosing and until follow-up 90-day post implant TEE. Aspirin monotherapy will be utilized in conjunction at 81 mg for up to 12 months, after which the patients will be exited from the study and further treatment decisions will be made by the following physician (see Schedule of Study Procedures at end of protocol). The objective of this trial is to evaluate safety and efficacy of a 90-day period of dabigatran etexilate following LAA closure to prevent device associated thrombus, while minimizing adverse bleeding by eliminating the need for clopidogrel. This is a single arm pilot study with the option (pending collaboration with additional funding source) to expand to a full single arm non-inferiority trial design with 80% power to detect a 1.4% difference with the non-inferiority margin 1% in absolute rate of DAT (control rate 3.9%).

Prospective, non-randomized single arm study. Comparison will be made to historical controls based on published one year DAT rates from PROTECT-AF, PREVAIL clinical trials, and EWOLUTION, and ACP/Amulet registries.

Echocardiography (TEE) will be performed at 90 days (3 months, +/- 2-week window), and again at 1-year post implant (+/- 4 weeks). Selected images will be interpreted by echo lab at coordinating center in an anonymous fashion (patient data de-identified). Ideal imaging will incorporate 0, 45, 90 and 135 degree angled views on the device at follow up.

Drug will be dispensed as part of the clinical trial supplied from the sponsor and each patient will receive a complete 90 days' supply up front. They will have a drug visit on the day of TEE with the research coordinator to hand back any remaining dabigatran, with clear instruction to stop the drug and only take ASA following confirmation of closure on TEE (no peri-device leak on Doppler of >5mm). A decision to continue anti-coagulation post closure 90day TEE will be made by the physician discretion based on TEE findings. If thrombus is found at the 90 days TEE, anti-coagulation may be extended another 6 weeks with repeat TEE imaging to confirm clot resolution at the discretion of the investigator. In the unlikely event of embolization or Doppler leak >5mm, decision on extending anti-coagulation, or re-implanting a device will be made by the following physician.

Additional baseline data collection: Patient demographics, medical history, age, sex, and prior use of anti-coagulants or anti-platelet medications will be collected. CHADS 2 Vasc, and HAS-BLED score calculated. Main indication for LAA closure must be documented. Baseline CBC and BMP required on day of implant or up to 1 week pre-procedure (typical standard of care labs at time of implant). This will include a recent calculation of Creatinine Clearance (using Cockcroft Gault and using patients actual body weight) and dosing of study drug will be made in accordance (see below). Repeat PCV or hematocrit on the morning after Watchman LAAC implantation will be per hospital standard. PCV or hematocrit value pre-implant and at the post 90-day visit will be analyzed.

Calculation for dabigatran dosing:

$$CCr = \{ (140 - \text{age}) \times \text{weight in kg} \} / (72 \times \text{SCr}) \times 0.85 \text{ (if female)}$$

Implant procedure variables to collect include access site, sheath used for deployment (WAS), device size at implant and number of implant attempts. LA pressure mean if available. Presence of angiography contrast or Doppler Echo leak, thrombus, or pericardial effusion post implant will be recorded. At 90 days, TEE report findings and image review (standard of care) with drug dosing visit with research coordinator and return of any remaining study drug. 1 year TEE (standard of care) with a research exit visit with MD, physician extender, or research coordinator, with documentation of ASA tolerance, dosing, and any late bleeding episodes or hospitalizations (typically should be reported as AE/SAE when first knowledge of event is determined). TEE images will be sent to the primary study site (Vanderbilt University Medical Center) and core TEE lab will review to confirm presence or absence of DAT. In cases of CTA utilized for follow up, similarly images will be reviewed by chest radiology team at Vanderbilt.

Medication administration with 90 days of dabigatran to be dispensed by pharmacy ideally one time (180 capsules).

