Dosing regimen of dabigatran will be by FDA and pharmacokinetic labeling for dabigatran 150mg BID dosing if Creatinine clearance >30mL/min, and 75mg BID dosing if 15-30mL/min. This will be based on calculated CC by baseline labs performed on day of implant. Additional dosing adjustments per package insert for patients taking dronedarone 400mg BID, or ketoconazole will be made consistent with drug label. The majority of subjects will be expected to be on 150 mg BID for 90 days. Subjects on 75 mg twice daily dosing may be enrolled if renal function is stable in the range of 15-30mL/min. Aspirin 81 mg a day will be taken along with oral anticoagulation for 90 days followed by longer-term aspirin 81 mg daily aspirin dose. At the 90 days TEE follow up (3 months) a PCV or CBC will be drawn and compared to baseline PCV pre-LAA closure implant as an assessment of

indolent blood loss (there is expected intra-procedural blood loss from back bleed on access sheaths estimated 25-125mL).

Drug required for study: Initially start with 100 subject pilot study on therapy for 90 days, with option to expand to full non-inferiority study if collaborative funding is secured (IF study expands beyond pilot, estimate 262 subjects, 90 days on therapy). Estimate 80% or more subjects on 150mg BID dosing, and up to 20% subjects on 75mg BID dosing. With either the 100-subject pilot study, or optional expanded single arm study (262 patients) the objective is to establish a device associated thrombus (DAT) rate at 3 months and 1 year within 1.5% or less deviation from published DAT rates at 3.9% (Saw, J., et al). Comparison will be made to published data on Watchman LAA closure utilizing the 45-day warfarin after implant followed by six-month dual antiplatelet regimen, or registry data from European experience on Watchman and Amulet/ACP LAA closure systems.

Patients can be consented for the trial on the day of implantation or up to one month prior in clinic during consultation for LAA closure. This is an unblinded, single arm prospective study. Study exit visit will be coordinated with final twelve-month follow-up imaging after LAA closure implantation.

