### **Statistical Methods/Calculations:**

Statistical sample size calculation to establish comparable DAT rate with the prescribed regimen:

Available data for background on DAT;

Overall incidence of DAT was 3.9% (82 DAT for 2118 implanted devices)

Lempereur et al. Meta-Analysis [ref 19]: 30 studies describing DAT events were included in the analysis. The overall incidence of DAT was 3.9% (82 DAT for 2118 implanted devices). The median time from procedure to diagnosis of DAT was 1.5 months (IQR: 0-2.9). Most cases were diagnosed with transesophageal echocardiogram (TEE). The treatment consisted of low molecular weight heparin (LMWH) in 45.5% of cases, and oral anticoagulation (OAC) or other treatment modalities in 54.5%. Complete thrombus resolution was achieved in 95.0% of cases (100% with LMWH and 89.5% with OAC). Treatment duration varied greatly with a median treatment duration of 45 days (IQR: 14-

135). Clinical events related to DAT consisted of neurologic events namely two transient ischemic attacks (2.4%) and four ischemic strokes (4.9%).

Saw et al [ref 7]. 339 analyzable TEE in follow up. Patients' mean age was  $74.4 \pm 7.5$  years, and 67.3% were men. The mean CHADS2 score was  $2.7 \pm 1.3$ , the mean CHA2DS2-VASc score was  $4.3 \pm 1.5$ , and the mean HAS-BLED score was  $3.0 \pm 1.2$ . Peri-procedural major adverse events occurred in 2.4%. Median clinical follow-up duration was 355 days (range 179 to 622 days). Follow-up transesophageal echocardiography was performed after a median of 134 days (range 88 to 227 days). Device-associated thrombus was observed in 3.2% Independent predictors of device-associated thrombus were smoking (odds ratio: 5.79;  $p = 0.017$ ) and female sex (odds ratio: 4.22;  $p = 0.027$ ).

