Kaneko et al. [ref 20] 78 patients (50 males,  $72 \pm 8$  years, average CHA2DS2-VASc score of  $4.3 + 1.8$ ) who had undergone WATCHMAN implantation. WATCHMAN was successfully implanted in all patients and four (5%) developed DRT. Patients with DRT were more often female (75 vs. 34%,  $p = 0.094$ ). CHA2DS2-VASc score was higher for patients with DRT ( $6.3 \pm 2.5$  vs.  $4.2 \pm 1.7$ ,  $p = 0.022$ ). Chronic kidney disease (100% vs. 43%,  $p = 0.024$ ) and deep implantation of the device, which was defined as implant position below the LAA ostial plane (75 vs. 24%,  $p = 0.026$ ), were more common in patients with DRT. HAS-BLED score ( $4.5 \pm 1.0$  vs.  $3.5 \pm 1.1$ ,  $p = 0.074$ ) was higher and oral anticoagulants (50 vs. 84%,  $p = 0.086$ ) were less commonly prescribed for patients with DRT. Multivariable logistic regression analysis showed that higher CHA2DS2-VASc score ( $p = 0.022$ , OR 2.8) and deep implantation ( $p = 0.032$ , OR 24.7) were associated with DRT. These results suggest the possible role of CHA2DS2-VASc scores and implantation depth in the development of DRT after percutaneous LAA closure using the WATCHMAN device.

With a single arm non-inferiority trial design to show the absolute rate of DAT is less than the control rate of 3.9% by a non-inferiority margin of 1% having a power 80% to detect a 1.4% difference at 0.05 level of significance, we would need 262 total subjects enrolled and reaching imaging endpoint evaluation. The initial study will begin with pilot to 100 subjects (with 46% power) with an option to expand if additional funding source is obtained.

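### The non-inferiority test is sized on a pooled 3.9% rate plus 1%, but the comparison text names other sources and a second 1.5% criterion, and nothing says which governs.

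*Combined protocol and SAP*

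**What the plan says.** The combined protocol and SAP describes the benchmark in three places.

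- **Sizing.** Section 2 describes the optional expanded trial as having 80% power "with the non-inferiority margin 1% in absolute rate of DAT (control rate 3.9"%). Statistical Methods/Calculations repeats the design as showing a rate "less than the control rate of 3.9% by a non-inferiority margin of 1"%. The operating characteristics are given there as "having a power 80% to detect a 1.4% difference at 0.05 level of significance", and the section concludes that "we would need 262 total subjects enrolled and reaching imaging endpoint evaluation". On the committed study it says: "The initial study will begin with pilot to 100 subjects (with 46% power"). The 3.9% is 82 events in 2118 devices from a 30-study meta-analysis, for which it reports: "The median time from procedure to diagnosis of DAT was 1.5 months (IQR: 0-2.9").
- **Comparison, Section 2.** The next paragraph reads "Comparison will be made to historical controls based on published one year DAT rates from PROTECT-AF, PREVAIL clinical trials", followed by EWOLUTION and the ACP/Amulet registries. The meta-analysis is not in that list.
- **Comparison, Section 3** (the drug-supply paragraph after the exclusion criteria). For both the pilot and the expansion, the objective is a DAT rate at 3 months and 1 year within 1.5% of a published 3.9%. That figure is attributed to the Amplatzer Cardiac Plug (ACP) study, which Section 1 and Statistical Methods both report as 3.2%. The comparator is then Watchman data on warfarin followed by dual antiplatelet therapy, "or registry data from European experience on Watchman and Amulet/ACP LAA closure systems".

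The primary endpoint is DAT at 1-year imaging. Section 1 gives 3.7% at one year for EWOLUTION. No DAT rate is given for PROTECT-AF or PREVAIL.

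**The concern.** In an unblinded single-arm study the historical benchmark is the whole control arm. Here the rate used for sizing and the rates named for comparison differ in source, in time point and, where quoted, in value. Two tolerances, 1% and 1.5%, stand side by side. No text defines the final test, the interval method, a rule for selecting or pooling comparators, or which statement takes precedence. An analyst who followed the comparison sentences literally would test against a limit the study was not sized for, and a result of a few events could pass under one sentence and fail under another.

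**Working it through.** **Inputs.** Control rate 3.9%, margin 1%, difference 1.4 points (true rate 3.9% − 1.4% = 2.5%), power 80%, level 0.05, N = 262, pilot n = 100 with 46% power (Section 2; Statistical Methods/Calculations). EWOLUTION 3.7% (Section 1). ACP 3.2% (Section 1; Statistical Methods). Alternative tolerance 1.5% (Section 3).

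**Step 1: reproduce the plan's figures.** One-sample normal approximation, with variance at the true rate p1 and limit L = 3.9% + 1% = 4.9%:

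n = (z0.95 + z0.80)² × p1(1 − p1) / (L − p1)² = (1.645 + 0.842)² × 0.025 × 0.975 / 0.024² = 261.6, rounded up to 262.

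Power(n) = Φ[(L − p1)/√(p1(1 − p1)/n) − 1.645].
- n = 262: Φ(2.488 − 1.645) = 80.0%.
- n = 100: Φ(1.537 − 1.645) = 45.7%, stated as 46%.

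Both figures reproduce. Sidedness is not stated. A two-sided 0.05 gives 333 subjects and 33.6% pilot power, so one-sided 0.05 is inferred. Taking the margin below the control rate (limit 2.9%), as the Statistical Methods wording literally reads, would need 9,419; a limit of 3.9% would need 769. The limit that fits the plan's own numbers is 4.9%.

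**Step 2: apply the other documented benchmarks.** The true rate stays at 2.5% and the formula is unchanged. The passing count is the largest x for which the one-sided 95% upper limit is below L. The Wald limit, x/n + 1.645√[(x/n)(1 − x/n)/n], matches the protocol's formula; exact binomial counts are shown for comparison.

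| Benchmark | Limit | N for 80% | Formula power, n = 262 | Passing count, n = 262: Wald (exact) | Passing count, n = 100: Wald (exact) |
|---|---|---|---|---|---|
| ACP 3.2% + 1% | 4.2% | 522 | 55% | 6 (5) | 1 (0) |
| EWOLUTION 3.7% + 1% | 4.7% | 312 | 74% | 7 (6) | 2 (1) |
| Pooled 3.9% + 1% | 4.9% | 262 | 80% | 8 (6) | 2 (1) |
| Pooled 3.9% + 1.5% | 5.4% | 180 | 91% | 9 (7) | 2 (1) |

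Wald upper limits behind the counts for n = 262: 6 events 3.81%, 7 events 4.31%, 8 events 4.80%, 9 events 5.29%, 10 events 5.76%. For n = 100: 1 event 2.64%, 2 events 4.30%, 3 events 5.81%.

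**Step 3: read across.** With 262 subjects, 7, 8 or 9 events by Wald (6 or 7 by the exact method) pass or fail depending on which statement is applied. With 100 subjects, only the ACP limit changes the count. PROTECT-AF and PREVAIL cannot be placed in the table because the documents give no rate for them.

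**The case against.** The strongest reply is that a benchmark is stated. Section 2 and Statistical Methods both put the non-inferiority design on 3.9% with a 1% margin, Section 3 also anchors its objective to 3.9%, and 4.9% is the limit that reproduces the stated N and pilot power. No text attaches the 1% margin to any other rate, and the comparison sentences could be meant as descriptive context. All of that stands, and it rules out some stronger readings.

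- A reader might infer that the pass mark is wholly open and can be picked once the data are in. The documents do not support that: 3.9% appears as the benchmark in three places. The fault is contradictory text with no order of precedence.
- A reader might infer that a more favourable comparator is there for the taking. The named sources with a quoted rate, 3.2% and 3.7%, give stricter limits than 3.9%, and by the exact method 3.7% and 3.9% share the same cut-off. The 78-patient Watchman series (4 events, 5%) would loosen the limit, but it is cited as background and is not among the named comparators.
- The 262-subject figures belong to an expansion that depends on funding. For the committed pilot no formal test is defined; only the 1.5% objective applies.
- The title of the cited meta-analysis covers Watchman, ACP and Amulet, so its 3.9% may overlap the named sources. The documents do not show how far.

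The reply does not remove the conflict. The sentences that say what will be compared name sources other than the one used for sizing, and the 1.5% criterion is a separate, looser figure.

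**Conclusion.** The point holds as an unreconciled contradiction about the benchmark and the margin. In the expanded study it moves the passing count from 6 to 9 of 262 by Wald (5 to 7 exact) and formula power from 55% to 91%, around a planned 8 events and 80%. In the pilot the effect is confined to the ACP rate: 1 event instead of 2 by Wald, 0 instead of 1 exact.

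This rests on one-sided 0.05 (inferred from the sample size), a true rate of 2.5% held fixed across benchmarks, and reading the 1.5% deviation as a margin added to 3.9%. The power figures are normal-approximation values and belong with the Wald counts. Under the exact cut-off of 6 events at 4.9%, the chance of passing at a true 2.5% is 51.8%, so the interval method also needs to be named.

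A reader might also infer that the plan claims non-inferiority to the labelled warfarin-then-antiplatelet regimen. It states no such conclusion. Section 3 names that regimen as one possible comparator, and a pooled rate across devices would not support such a claim if it were made later.

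**What to change.** In Section 2, Section 3 and Statistical Methods/Calculations:

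1. State one primary comparison: the fixed pooled rate of 3.9%, with its source and the timing of its events, and a 1% margin. Success is a one-sided 95% upper limit below 4.9%. Name the interval method. Reword the Statistical Methods sentence so that it cannot be read as a limit of 2.9%.
2. Remove the 1.5% criterion or reconcile it with the 1% margin, and say what, if anything, is tested in the 100-subject pilot.
3. Correct the source given for 3.9% in Section 3.
4. Label PROTECT-AF, PREVAIL, EWOLUTION, the ACP/Amulet registries and labelled-regimen Watchman data as descriptive context.
5. Word any conclusion as a comparison with the pooled historical rate, not with the labelled regimen.

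The cost is wording only; with the 4.9% limit kept, the planned N does not change. The sponsor gives up flexibility in choosing comparators. If an exact interval is chosen, its lower power at 262 subjects should be acknowledged.

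### The 3.9% control rate includes thrombi diagnosed before the trial's first follow-up image, so early DAT that clears counts in the control but not in the trial arm

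*Combined protocol and SAP*

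**What the plan says.** **Trial imaging.** Section 2 (Study design): "Echocardiography (TEE) will be performed at 90 days (3 months, +/- 2-week window), and again at 1-year post implant (+/- 4 weeks". Study drug starts the morning after implant and is "taken BID per package insert dosing and until follow-up 90-day post implant TEE". The Schedule of Study Procedures also lists an intra-operative TEE and an as-needed column for adverse events and DAT, but no routine image between implant and the 90-day visit. Section 2 records thrombus seen after implant among the procedure variables. The Endpoints section defines the primary endpoint as DAT at 1-year imaging. The drug-requirement text in section 3 speaks of a rate at 3 months and 1 year.

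**Control rate.** Statistical Methods/Calculations: "The overall incidence of DAT was 3.9% (82 DAT for 2118 implanted devices". For the same pooled source: "The median time from procedure to diagnosis of DAT was 1.5 months (IQR: 0-2.9" months). It also reports that "Complete thrombus resolution was achieved in 95.0% of cases (100% with LMWH and 89.5% with OAC"). Section 1 describes the label regimen, in which "ASA 81mg is to be taken to 45 days when a follow up TEE is performed to assess leaks, device position or thrombus formation".

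**Test.** The design is described as "With a single arm non-inferiority trial design to show the absolute rate of DAT is less than the control rate of 3.9" percent, with a 1% margin, 80% power to detect a 1.4% difference at the 0.05 level, 262 subjects, and a 100-subject pilot with 46% power. Section 2 repeats the 3.9% as the control rate, and section 3 makes it the reference for both sample sizes.

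**Later-looking sources.** For the Amplatzer Cardiac Plug registry (DAT 3.2%): "Follow-up transesophageal echocardiography was performed after a median of 134 days (range 88 to 227 days"). Section 1 gives a 1-year rate of 3.7% for the EWOLUTION registry.

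**The concern.** DAT can appear, be treated and disappear, so the rate found depends on when one looks. The pooled 3.9% collects DAT whenever it was diagnosed, much of it in the first weeks. The trial's first follow-up look comes after about eleven weeks of anticoagulation. A thrombus that forms early and is gone by then is an event on the control side and nothing on the trial side. No part of the plan adjusts the 3.9% for this or restricts it to DAT visible at the trial's imaging times.

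The error runs one way: it lowers the trial's observed rate relative to the benchmark. At stake is what a pass against 3.9% means. Part of an apparent gain could come from the imaging calendar rather than the regimen, and the nominal 0.05 error would not hold.

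**Working it through.** **Step 1. Reproduce the plan.** Inputs from Statistical Methods/Calculations: control 3.9%, margin 1%, difference 1.4%, level 0.05. Inferred: limit 3.9% + 1% = 4.9%, assumed true rate 3.9% − 1.4% = 2.5%, one-sided test.

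n = p(1 − p) × [(1.645 + 0.842) / (limit − p)]² = 0.025 × 0.975 × (2.487 / 0.024)² = 261.6, so 262.

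Power = Φ[(limit − p) / √(p(1 − p)/n) − 1.645], which is 80.0% at 262 and 45.7% at 100. Both match the plan, so this is its formula.

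**Step 2. Put the two calendars side by side** (30.44 days per month).
- Benchmark median: 1.5 × 30.44 = day 46. Upper quartile: 2.9 × 30.44 = day 88.
- Trial's first follow-up image: 90 − 14 = day 76 at the earliest.
- Day 76 lies between the median and the upper quartile, so 50% to 75% of timed benchmark DAT were diagnosed before it. That is about 41 to 62 of 82, if timing was available for all 82.
- The lower quartile is 0, so at least a quarter was diagnosed around implant. The trial images then too, but thrombus seen at that point is a procedure variable and is not counted by the primary endpoint.

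The mismatch remains whether the trial counts DAT at 1 year only or at 3 months and 1 year. It is wider if only 1 year counts.

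**Step 3. Effect on the false-pass rate.** Let s be the share of DAT that the trial would not see because it cleared before the look. A regimen truly at 4.9% then shows 4.9% × (1 − s). The documents do not give s. One illustration uses the plan's later-imaged rate: s = 1 − 3.2/3.9 = 18%. The 6% and 25% rows are assumptions: a quarter of DAT falling in the gap, with a quarter (0.25 × 0.25) or all of it clearing.

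N = 262, limit 4.9%. The exact rule passes with at most 6 DAT.

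| s | Observed rate | Pass, normal formula | Pass, exact |
|---|---|---|---|
| 0 | 4.90% | 5.0% | 2.6% |
| 6% | 4.61% | 8% | 4% |
| 18% | 4.02% | 18% | 9.6% |
| 25% | 3.68% | 28% | 15% |

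For the 18% row: (0.049 − 0.0402) / √(0.0402 × 0.9598 / 262) = 0.0088 / 0.0121 = 0.73, and Φ(0.73 − 1.645) = 18%. At N = 100 the standard error is 0.0196, and Φ(0.45 − 1.645) = 12% instead of 5%.

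**Step 4. Power on a matched scale.** With a 3.2% control and a 1% margin the limit is 4.2%. The assumed true rate must move to the same scale: 2.5% × 3.2/3.9 = 2.05%. The Step 1 formula then gives 79% at 262 and 45% at 100.

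**The case against.** The case against a large effect is strong, and much of it stands.

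- Day 90 is the first follow-up image, not the first image of any kind. There is an intra-operative TEE, and triggered imaging is allowed.
- An early thrombus that persists to days 76–104 is seen. Only those that clear or embolise first are missed.
- The 89.5% resolution on oral anticoagulation describes DAT that was diagnosed and then treated. It does not describe a thrombus that forms on dabigatran and clears on the same regimen.
- The benchmark times are times of diagnosis under other regimens. An early thrombus that dabigatran prevents is treatment effect, not missed detection.
- The plan's later-looking sources still report 3.2% and 3.7%. The 3.2% of 339 TEEs is about 11 events, with an exact 95% interval of 1.6% to 5.7%, which includes 3.9%. The 18% loss is therefore itself uncertain and could be nil.
- The formal non-inferiority test belongs to an optional, unfunded expansion, and section 2 also names published one-year rates as controls.

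These points limit the size. They do not remove the mismatch or change its direction. The 3.9% is the control rate in sections 2 and 3 and in the sample-size paragraph, and section 3 applies it to the 100-subject pilot as well.

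A reader might infer that at least half of control-type DAT would go unseen in the trial. The documents support only that at least half was diagnosed before day 76, which is a different quantity.

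**Conclusion.** The concern holds as a one-directional bias of unknown size. The control rate counts DAT from a period that the trial's endpoint does not observe, and the plan makes no allowance for it. With the 18% illustration, the false-pass rate at N = 262 rises from 5% to about 18% (normal formula), or from 2.6% to 9.6% (exact). Assumed losses of 6% to 25% give 8% to 28%, or 4% to 15% exact. These figures rest on the inferred 4.9% limit, a one-sided test, an assumed unseen share and, for the 18%, on attributing a between-device difference wholly to timing.

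Two stronger readings are not supported. One applies the 89.5% clearance to half of all DAT and arrives at a false-pass rate near 70%; that figure concerns treated, diagnosed thrombi. The other keeps the true rate at 2.5% against a 4.2% limit and concludes that power is really 55% and 29%. That adjusts only the control side. With both sides adjusted, power is 79% and 45%, close to the plan's own.

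**What to change.** No image or visit needs to be added.

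1. In section 2, section 3 and Statistical Methods/Calculations, state that the 3.9% includes DAT diagnosed before the trial's first follow-up image, and call the comparison with it descriptive.
2. Base the inferential comparison on rates from comparable imaging times. Candidates already in the plan are the 1-year 3.7% and the 3.2% imaged at 88–227 days. Check first which images the 3.7% rests on, since the plan does not say. Diagnosis times re-extracted from the pooled source would serve if they can be obtained, but it combines 30 studies and may not allow it.
3. Pre-specify a sensitivity analysis over the unseen share s. For example, test against 4.9% × (1 − s) for s from 0 up to the 75% ceiling, and report the value at which non-inferiority is lost.
4. State which trial images count toward the rate, then recompute limit and power with the control rate and the assumed true rate on that same imaging scale.

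The cost is rewording, one added analysis and possibly some data extraction. The downside is a benchmark that rests on fewer events and, for the 3.2%, on a different device.
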